3.0 Objectives

The purpose of this study is to determine whether there is clinical evidence to support the use of Mindfulness-Based Stress Reduction as a treatment for Veterans with Chronic Multi-Symptom Illness: pain, fatigue, and cognitive or mood disturbances.

Hypothesis One (re: outcomes): Participants randomized to CDSMP will derive benefit for the primary outcomes, but with smaller effects than the participants randomized to MBSR. We hypothesize that Veterans randomized to MBSR will report significantly greater reduction in each of the three primary outcome measures (pain, fatigue and cognitive failures) at 6-month follow-up as compared to aCDSMP.

Hypothesis Two (re: acceptability): MBSR will be an acceptable and satisfactory program for Veterans with CMI, as indicated by attendance rates, a self-report measure of satisfaction, and qualitative interviews. We hypothesize that Veterans with CMI randomized to MBSR will report greater satisfaction with care than their peers randomized to CDSMP.

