The active control, aCDSMP, will account for the non-specific elements of MBSR (e.g. group support, positive expectancy). The standard CDSMP program is a group-based 6 session, 2.5 hour per session program. For this study, we added three sessions after the completion of standard CDSMP so that each intervention will be of identical duration and structure. Fidelity coding from audiotapes will evaluate protocol adherence for both MBSR and CDSMP. Similar to MBSR, CDSMP is taught by trained, experienced facilitators who believe in the benefit of the program; allegiance of researchers or therapists has been shown to be a predictor of treatment outcomes.

Risk and Benefit: The risks for this study involve the potential for psychological distress associated with collection of self-report data and the qualitative interview, and the possibility that undergoing either the MBSR class or CDSMP could be stressful and worsen symptoms. Further, there is a risk that MBSR and CDSMP will not be efficacious for some individuals. We plan to educate patients about the possible risks and benefits prior to study enrollment by providing a thorough orientation to the research and an overview of each intervention prior to giving informed consent. Potential benefits for those randomized to either condition may take the form of reduced CMI symptoms, and increased health-related quality of life. Veterans' families may also benefit as a result of the shift in emotional state. However, a participant may not benefit directly from participation in the study. Information gained in the study may be of benefit in the future to persons with CMI. Specific measures for minimizing risk are outlined below.

Procedures to Minimize Risk to Subjects and Protect Confidentiality:

- 1) Group sessions will include reminders to patients that they can choose what they will and will not do, and that it can be flexible in meeting an individual's needs (e.g. in MBSR a patient may meditate with eyes open, choose not to lie down, shorten the meditation time, choose not to practice some of the yoga postures, etc., while in aCDSMP a patient may choose to share more or less of their personal material with the group, etc.)

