5.2 Recruitment Methods

The recruitment goal is 308 total, at least half (n=154) of whom will be Gulf War Veterans with CMI. The remaining subjects will be non-GW Veterans with CMI.

In order to provide groups that are the same size as typically offered for both MBSR and CDSMP, we plan to form MBSR/aCDSMP groups of up to 18 participants per MBSR or aCDSMP group until 30 Veterans per cohort have been recruited (i.e., 30 Veterans will be recruited per research cohort, and we will randomize participants until 30 total Veterans per cohort are enrolled or one intervention reaches 18 participants, whichever occurs first; these 30 Veterans will be randomized in equal proportion to MBSR or aCDSMP). (As of July 2020 groups will be capped at 10 per group, in order to meet the recommended class size for remote instruction.) However, in order to allow us to answer additional scientific questions about CMI outcomes among non-GW Veterans, and because we think it could be challenging to form cohorts comprised entirely of GW Veterans (which would require recruitment of 30 GW Veterans per cohort), we designed the study so that only approximately half of each cohort (15 Veterans) will be GW Veterans. (10 GW Veterans post July 2020) The remaining 15 Veterans in each cohort will be Veterans who meet all other inclusion / exclusion criteria (including presence of CMI) but who were not deployed during the GW. The non-GW Veterans will complete the same study measures at the same points as described for GW Veterans throughout this application, but non-GW Veterans are not considered in the power calculations for the primary study hypotheses. We think that this approach provides the ability to answer additional questions (described below) while simultaneously enhancing the feasibility of the study.

The recruitment strategy described above affords several practical and theoretical advantages, including: 1) it will allow groups of sufficient size (30 Veterans per cohort) to be formed more easily, which will assure that there will be enough participants in each study cohort to allow the groups to proceed; 2) as part of an

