5.6 Data Analysis

We powered the study to detect a between group effect size Cohen's $d \geq 0.50$ for each of the primary outcome measures. An effect size $d = 0.5$ represents a medium effect, and a change smaller than $d=0.50$ has been advocated as a reasonable threshold of clinical significance when assessing patient reported outcomes, including pain and physical and emotional functioning.⁸ The literature (see section on MBIs for CMI), and our pilot data (preliminary studies section) suggest medium to large effect sizes for CMI, supporting the feasibility of detecting this level of difference. Although effect sizes derived from small samples are inherently unreliable,⁷ we included effect sizes from our pilot work as part of a broader review of the literature on outcomes of CMI symptoms after MBIs. As described above, the ability to detect a medium effect

size is supported by evidence of only modest effects in the proposed comparison condition. Overall, we think that powering the study to detect a difference of $d=0.50$ or greater between arms is conservative and clinically relevant.

Assuming a between group effect size of at least $d=.50$, equal allocation to either intervention, a two-sided $\alpha = 0.05$, and $\beta = 0.20$, at least 64 GW Veterans are required in each randomization arm.⁹⁷ To protect against the effects of attrition, we added 20% to this final sample size for a recruitment goal of 154 GW Veterans with CMI. This attrition estimate is conservative; it is slightly greater than in our pilot RCTs comparing MBSR to TAU.³ The sample size required *per arm* of the study (at 80% and 90% power) is presented across a range of effect sizes (Table 3).⁹⁷

Intraclass correlation (ICC): our pilot study of MBSR for GW Veterans (preliminary studies) showed an ICC for primary outcomes of $\rho= 0.00$ at follow-up. Because our data do not indicate significant ICCs for any of the primary outcome measures, the proposed analyses do not incorporate ICC results and are not powered to account for them.

Qualitative data will be coded (a sort of pre-analysis) continuously as participants complete their qualitative interviews; when saturation is reached, and no new codes are being generated, the research team will stop conducting the interviews and begin to analyze the qualitative data more extensively. The Project Manager and [name] will be primarily involved in the qualitative data analysis.

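### Section 5.6 sets within-class correlation to zero because of a small MBSR-versus-usual-care pilot; if enough of any correlation is specific to a class, type I error rises modestly above 5% and the 80% power does not hold

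*Combined protocol and SAP*

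**What the plan says.** Section 5.6 (Data Analysis) requires 64 GW Veterans per arm for d = 0.50, two-sided alpha 0.05 and 80% power, and adds 20% to reach 154. It then reports an ICC of 0.00 at follow-up from the MBSR pilot in GW Veterans. The reason it gives is this: "Because our data do not indicate significant ICCs for any of the primary outcome measures". From that it draws the rule that "the proposed analyses do not incorporate ICC results and are not powered to account for them". A little before this, the same section remarks that "effect sizes derived from small samples are inherently unreliable".

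Sections 2.0 (Introduction) and 5.2 (Recruitment Methods) describe the pilot as 55 randomised GW Veterans, with usual care as the comparator. The text supplied gives no number of pilot classes, no split by arm and no interval for the ICC.

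In this trial both arms are delivered in groups. On in-person cohorts, Section 5.2 says "these 30 Veterans will be randomized in equal proportion to MBSR or aCDSMP" and "only approximately half of each cohort (15 Veterans) will be GW Veterans", changing to 10 GW Veterans per cohort after July 2020. Hypothesis One in Section 3.0 predicts a greater reduction in "each of the three primary outcome measures (pain, fatigue and cognitive failures) at 6-month follow-up as compared to aCDSMP". No class or cohort term, cluster-robust method or sensitivity analysis for clustering appears in the text supplied.

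**The concern.** A non-significant ICC from a small pilot is treated as an ICC of exactly zero. The same section distrusts effect sizes from small samples, yet an ICC is harder still to estimate from few classes. The pilot also cannot speak for aCDSMP, which makes up half of the classes here.

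If people in the same class have correlated outcomes for reasons particular to that class, the arm difference varies more than an unclustered analysis assumes. Intervals are then too narrow and the test rejects too often under the null, for each of the three primary symptom comparisons. The stated 80% power then does not belong to a test that holds 5%.

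**Working it through.** **1. The plan's own figure.** For d = 0.5, two-sided 0.05 and 80% power, the t-test solution is 63.77, so 64 per arm (power 80.1%). Then 128 × 1.2 = 153.6, so 154. Both figures imply a design effect of 1.

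**2. What the pilot can exclude.** Only its MBSR arm had classes. Assume 27 people in k = 3 to 6 classes of m = 27/k (neither figure is stated). The upper 95% limit is (FU − 1)/(FU − 1 + m), where FU = F/F(0.025; k − 1, k(m − 1)).
- F = 1 (estimate exactly zero): k = 3 gives FU = 1/0.0253 = 39.5 and limit 38.5/47.5 = 0.81; k = 6 gives FU = 1/0.158 = 6.31 and limit 5.31/9.81 = 0.54.
- F = 0.5 (a negative estimate reported as zero): 0.68 and 0.32.
- If the true ICC were 0.05, a 5% test on one outcome would be non-significant 88–90% of the time. All three outcomes would be non-significant 68–74% of the time if independent, and more often if correlated.

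A non-significant 0.00 is therefore the likely report whether or not a modest ICC exists.

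**3. Class size in the primary GW comparison.** 15 or 10 GW Veterans per cohort over two classes gives 7.5 or 5 per class. Scaling to completers by 64/77 gives 6.2 and 4.2, so the range used is m = 4 to 6.25.

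**4. Type I error when class is ignored.** Veterans are randomised within cohorts, so variation common to a cohort's two classes cancels from the arm difference. If a share s of the ICC is class-specific, the true variance relative to the assumed variance is V = 1 + ICC × (m·s − 1). This exceeds 1 only when s > 1/m, which is 25% at m = 4 and 16% at m = 6.25. Type I error = 2 × [1 − Φ(1.96/√V)]. The ICC values are assumptions, and an unadjusted t-test is taken as implied by the sample-size formula.

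| Share class-specific | ICC 0.02: V | Error | ICC 0.05: V | Error |
|---|---|---|---|---|
| 100% | 1.06–1.105 | 5.7–6.2% | 1.15–1.2625 | 6.8–8.1% |
| 50% | 1.02–1.0425 | 5.2–5.5% | 1.05–1.106 | 5.6–6.2% |
| 0% | 0.98 | 4.8% | 0.95 | 4.4% |

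Simulation of the unadjusted t-test (100,000 trials per setting) agrees: 5.6–6.1% and 6.8–8.0% when wholly class-specific, 5.3–5.4% and 5.5–6.3% at half. With 16 classes of 4 per arm and a total ICC of 0.05, it gives about 4.7% at a 10% share, 5.0% at 25% and 5.6% at 50%. Simulated coverage of the unadjusted 95% interval, with the ICC wholly class-specific, is 94.0–94.5% at 0.02 and 92.0–93.1% at 0.05.

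**5. Power of a test that keeps 5%.** Noncentral t with ncp = 0.5 × √(64/(2V)), s = 100%.
- 126 df: 76.1–77.8% at ICC 0.02 and 70.5–74.5% at 0.05.
- Class-level df, 128/m − 2 = 30 and 18.5: 72.2–75.8% and 66.5–72.3%, against 76.4–78.1% at ICC 0.

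At d = 0.5 the unadjusted test still rejects about 79–80% of the time. The damage is therefore to error control and coverage, not to the chance of a positive result.

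**The case against.** The strongest reply is that no non-zero ICC is documented anywhere, and that the only data cited gave zero. At an ICC of 0.02 the worst case is barely above 6%. The grant's preliminary-studies section, which Section 5.6 cites, is not in the supplied text and may give class counts or an interval. This stands as a limit on size and certainty. It does not rescue the rule, because the stated reason is non-significance, and a pilot of 55 people with usual care as comparator cannot inform aCDSMP classes.

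Two stronger readings are tempting, and neither is supported.
- A reader might infer that any class-specific correlation at all pushes the error above 5%. It does not: below a share of about 1/m, the gain from randomising within cohorts outweighs it, and the split between class and cohort is unknown.
- A reader might infer that the protocol itself predicts differences between classes. Section 5.1 says that "allegiance of researchers or therapists has been shown to be a predictor of treatment outcomes" and that the active control "will account for the non-specific elements of MBSR (e.g. group support, positive expectancy"). Both statements concern balance between the arms, not variation between classes of one arm. The text supplied does not say how many facilitators teach each arm. If one person taught every class in an arm, the teacher effect would be confounded with arm, and a class term would not remove it.

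It is also fair to object that a remedy should not settle the whole primary model. The fix is therefore confined to the clustering terms.

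**Conclusion.** The point holds in a limited form. Fixing the ICC at zero is not justified by the evidence that Section 5.6 cites, and the 80% power holds only at a design effect of 1. The omission is certain; inflation is conditional and modest. Type I error reaches about 6% at an ICC of 0.02 and 7–8% at 0.05 if the correlation is wholly class-specific. It is at most about 5.5% and 6.3% if half is shared by the cohort, and is not inflated if all is shared.

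These figures rest on 64 completers per arm, 4 to 6.25 GW completers per class, an unadjusted t-test (the plan names no model) and ICC values that the documents do not supply. They do not show that the trial's error rate is in fact above 5%.

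**What to change.** Replace the sentence in Section 5.6 with: *The primary between-arm model for each primary symptom outcome will include random intercepts for cohort and for class (cohort × arm), with small-sample degrees of freedom. Both terms are kept whatever their estimate or significance, and the class ICC is reported with its 95% interval.* Restate power for that model at ICC 0, 0.02 and 0.05. No added enrolment is proposed.

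The cohort term is needed: with a cohort-shared ICC of 0.05, a class-level test without it rejects only 2.7–3.2% under the null.

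This is a cheap improvement. Cohort and arm identify the class, and Section 5.6 places the quantitative analysis after the last cohort's final assessments. The cost, from simulation of a 6-month comparison with both random terms and no baseline covariate:
- Power at ICC 0 is 77.4–77.6%, against 80.4–81.5% for the unadjusted test, a loss of about 3–4 points. It is 74.8–76.1% at class-specific ICC 0.02 and 70.4–73.4% at 0.05.
- Intervals are wider by 4–6% at ICC 0, 6–9% at 0.02 and 8–14% at 0.05.
- Type I error is 3.6–5.4% over the settings tried.

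That simulation used equal class sizes and a balanced-design solution in place of Kenward-Roger degrees of freedom, so it should be repeated with realistic, unequal classes. The stated power will look less favourable. Adjusting for the baseline value of the outcome, which Section 5.5 already collects, is a separate gain that may offset some or all of the loss; how much depends on a baseline-to-follow-up correlation that the documents do not give.

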5.7 Withdrawal of Subjects

If the study subject becomes a threat to the safety of others in his or her treatment group, or to the research team, that subject's participation in the study will be withdrawn from the research without their consent.

If a subject wishes to withdraw from the study before all procedures are complete, he or she simply needs to notify the study's project manager, study coordinator, or other study team member by phone or in person that he or she no longer wishes to participate, and the subject will be withdrawn from the study and no longer contacted regarding study procedures. A primary study contact number will be provided

to each participant so they know how to reach the study team to request early withdrawal (or for any other questions).

6.0 Reporting

When an unexpected serious adverse event occurs, we will log it in an “Adverse Events & Problems” log, to be used for providing reports to the Data Safety Monitoring Board (DSMB), in addition to submitting a report to the IRB within 5 days as required. All other adverse events, problems, and protocol deviations will be logged and reported to the Safety Monitor and the IRB with annual reviews.

Adverse Events related to worsening depression symptoms will be actively monitored by tracking PHQ-9 scores. We will define as an AE an increase in PHQ-9 depression score by 2 or more severity categories. For example, if a patient experiences an increase in depression from moderate to severe, this would be an increase in two categories of severity. The PHQ-9 categorizes depression as none, mild, moderate, moderately severe, and severe according to the total score; this has been previously validated. At the midpoint of the study, the data monitor would then analyze whether significantly greater adverse events occur in one arm of the study, which might warrant stopping the study.

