Human Subjects Protocol

VA Puget Sound IRB

[MIRB 00873] A Randomized Clinical Trial of Group Interventions for Veterans with Chronic Multi-Symptom Illness

Funding Agency: VA HSR&D

Principal Investigator: [name]

Version 10; 7/7/2021

Abstract

The study will recruit and randomize up to 308 participants. Half (n=154) of these will be Gulf War Veterans who meet criteria for Chronic Multi-Symptom Illness (CMI), and the other half (n=154) will be Veterans from other periods of service who also meet criteria for CMI. Half of the Gulf War Veterans (n=77) and half of the non-Gulf War Veterans (n=77) will be randomly assigned to the Mindfulness-Based Stress Reduction (MBSR) group, and the other 154 participants (77 Gulf War Veterans, 77 non-Gulf War Veterans) will be randomly assigned to the augmented Chronic Disease Self-Management Program (aCDSMP) group. As of July 2020, these groups will be conducted remotely using the VA's Video Connect software, due to the restrictions resulting from the COVID-19 virus. Each of the group sessions are 2.5 hours long, and they meet once a week for 8-weeks, as well as once on a Saturday for 4 hours (between Week 6 and 7). As of July 2020, we will no longer be including Saturday sessions, given the difficulties of doing so in a remote learning format. Each cohort will randomize 30 subjects or until one intervention reaches 18 randomized participants, whichever occurs first. As of July 2020, groups are capped at 10 participants each, or 19 subjects randomized per cohort; this cap reflects ideal group sizes for the remote learning format.

Data will be collected from subjects during five assessments while they are enrolled in the study: 1) at Baseline, which will take place within 6 weeks prior to beginning MBSR or aCDSMP; 2) at "Midpoint," between Week 4 and Week 5; 3) at "Post," within a month following the completion of the group series; 4) at 3-months after the group ended; and 5) at 6-months after the group ended.

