At each of these assessments except the Midpoint, researchers will provide and administer self-report measures to the participants using a VA computer to assess changes in the following symptoms and attitudes over time and between the two study arms: pain, fatigue, cognitive failures, depression, PTSD, health- and mental-health-related quality of life, drug use, alcohol use and negative consequences, gastrointestinal distress, mindfulness, self-compassion, and decentering. These assessments can be completed both in person or by phone, as of March of 2020 all assessments will be completed by phone because of COVID-19 restrictions. At the Midpoint, participants complete a pen-and-paper set of questionnaires assessing potential mediations (e.g. mindfulness and self-efficacy) and primary endpoints, which will allow mediation analyses to be performed in the future.

At the Post Assessment, a qualitative interview will be conducted with Gulf War veterans to explore impressions of, and satisfaction with, the two different treatments (MBSR and aCDSMP). List of Abbreviations

CMI – Chronic Multi-Symptom Illness

GW – Gulf War

GWS – Gulf War Syndrome

MBSR – Mindfulness-based Stress Reduction

aCDSMP – adapted Chronic Disease Self-Management Program

CPRS – Computerized Patient Record System (electronic medical record)

PROMIS – Patient-reported Outcome Measures Information System

VVC- VA Video Connect

Contents

Protocol Title:.....	5
1.0 Study Personnel.....	5
2.0 Introduction.....	5
3.0 Objectives.....	8
4.0 Resources and Personnel.....	8
5.0 Study Procedures.....	10
5.1 Study Design.....	10
5.2 Recruitment Methods.....	14
5.3 Informed Consent Procedures.....	16
5.4 Inclusion/Exclusion Criteria.....	17
5.5 Study Evaluations.....	17
5.6 Data Analysis.....	20
5.7 Withdrawal of Subjects.....	21
6.0 Reporting.....	21
7.0 Privacy and Confidentiality.....	21
8.0 Communication Plan.....	22
9.0 References.....	23

Protocol Title: A randomized clinical trial of group interventions for Veterans with Chronic Multi-Symptom Illness

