5.5 Study Evaluations

(B=baseline; M=midway through treatment; P=post-treatment; 3=3-months post-treatment; 6=6-months post-treatment)

Measure/Data Collection Tool	Assessment	Purpose/Variable that the tool measures
Study Sample Description Data (describes subject population and generalizability of results)		
Demographic Information	B	Sample description, blocking (gender), moderators
Life Events Checklist (LEC)	B	Sample description; trauma history
Deployment Risk and Resilience Inventory (DRRI)	B	Wartime exposures
Rome III – IBS	B	Sample description, to indicate prevalence of Irritable Bowel Syndrome in sample
Eligibility Evaluation (inclusion/exclusion criteria)		
Chronic Multi-Symptom Illness (CMI) Questionnaire	B	Sample description, eligibility evaluation
MINI International Neuropsychiatric Interview V-5 (DSM-V)	B	Sample description, eligibility evaluation, SUD classification (possible moderator)

Medical history interview (seizures, delirium tremens)	B	Sample description; eligibility evaluation
Tracking		
Contact form	B, P, 3, 6	Updating subject contact information; retention
Primary Outcomes		
Short Form McGill Pain Questionnaire (SF-MPQ-2) total score	B, M, P, 3, 6	Pain
General Fatigue subscale of the Multidimensional Fatigue Inventory (MFI)	B, M, P, 3, 6	General fatigue symptoms
Cognitive Failures Questionnaire (CFQ)	B, M, P, 3, 6	Concentration and memory disturbances
Client Satisfaction Questionnaire (CSQ-8)	P, 6	Satisfaction with the group (MBSR or aCDSMP)
Qualitative Interviews	P	Data merging and mixed methods techniques, used to analyze patient impressions of, and levels of satisfaction with, MBSR and aCDSMP
Secondary Outcomes		
Patient Health Questionnaire (PHQ-9)	B, P, 3, 6	Depressive symptoms
PTSD Checklist – Civilian Version (PCL-C)	B, P, 3, 6	Post-traumatic Stress Disorder symptoms
SF-12 (Mental and Physical Component Summary Scores)	B, P, 3, 6	Health-related quality of life
Drug Abuse Screening Test (DAST) for drug use other than alcohol or tobacco	B, P, 3, 6	Drug use: frequency and severity
NIH Patient Reported Outcome Measures Information System (PROMIS) for Alcohol Use and Negative Consequences, short form	B, P, 3, 6	Substance Use Disorder (SUD) symptom severity for alcohol
NIH Patient Reported Outcome Measures Information System (PROMIS) for Gastrointestinal	B, P, 3, 6	Gastrointestinal Symptoms, including IBS

Distress		
Potential Mediators		
Pain Self-Efficacy Questionnaire (PSEQ)	B, M, P, 3, 6	

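### The PHQ-9 is the stated monitor for worsening depression, but none is scheduled while the classes run, so the PHQ-9-defined adverse event cannot be detected during exposure

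*Combined protocol and SAP*

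**What the plan says.** Section 6.0 names one active monitor for depression: "Adverse Events related to worsening depression symptoms will be actively monitored by tracking PHQ-9 scores". The event is then defined: "We will define as an AE an increase in PHQ-9 depression score by 2 or more severity categories". The same section has the data monitor compare adverse events between arms once, halfway through the study, and says that an excess in one arm could be grounds to stop.

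The table in Section 5.5 lists the measure as "Patient Health Questionnaire (PHQ-9) B, P, 3, 6 Depressive symptoms", with no M for Midpoint. The Abstract agrees. The battery that includes depression is introduced with "At each of these assessments except the Midpoint, researchers will provide and administer self-report measures to the participants", and the class Midpoint is described separately: "At the Midpoint, participants complete a pen-and-paper set of questionnaires assessing potential mediations", together with the primary endpoints.

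Section 5.1, under risk and benefit, lists among the study risks "the possibility that undergoing either the MBSR class or CDSMP could be stressful and worsen symptoms". Section 5.7 says that a person who withdraws from the study is not contacted again about study procedures. No PHQ-9 at early termination is described.

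**The concern.** The risk that the plan names arises from attending the classes. The instrument chosen to detect it is not given while they are attended. Three consequences follow.

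- The defined event can first be recorded only after the class series has ended.
- A participant who worsens by two categories and recovers by Post is not counted by this definition.
- A participant who withdraws from the study before Post has no score to set against baseline, so the definition cannot be applied.

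The between-arm comparison in Section 6.0 draws on these events and may lead to stopping, so incomplete ascertainment matters for more than description. If people who tolerate their class poorly are also more likely to leave the study, the missing scores would fall where harm is most likely. That is plausible, but the documents do not show it.

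**Working it through.** The plan states no figure to reproduce here. The check compares the schedule with the assessment windows.

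**Inputs**
- PHQ-9 occasions: B, P, 3, 6 (Section 5.5).
- Baseline: 0 to 6 weeks before the first class (Abstract: "which will take place within 6 weeks prior to beginning MBSR or aCDSMP").
- Class series: 8 weekly sessions, taken as 8 weeks (Abstract).
- Class Midpoint: between Weeks 4 and 5, so about 4 weeks after the first class (Abstract).
- Post: 0 to 1 month after the series ends; 1 month = 30.4/7 = about 4.3 weeks (Abstract).
- Sample size: 64 per arm, raised by 20% to 154 Gulf War Veterans (Section 5.6).

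**Timing under the current schedule**
- PHQ-9 readings during the classes: 0 of 4 occasions.
- First class to first post-baseline PHQ-9: 8 + 0 = 8 weeks, to 8 + 4.3 = 12.3 weeks.
- Baseline PHQ-9 to first post-baseline PHQ-9: 0 + 8 + 0 = 8 weeks, to 6 + 8 + 4.3 = 18.3 weeks.

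The 18.3 weeks is the worst case and includes up to 6 weeks before any exposure. Counting from the day of the first session to the day of the eighth (7 weeks) would lower each figure by one week.

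**Timing with a Midpoint PHQ-9**
- First class to first post-baseline PHQ-9: about 4 weeks.
- Baseline to Midpoint: 0 + 4 = 4 weeks, to 6 + 4 = 10 weeks.
- Midpoint to Post: 8 - 4 = 4 weeks, to 12.3 - 4 = 8.3 weeks.

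**How many could lack a post-baseline score**

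The documents give no rate of loss before Post, only an overall attrition allowance, which also covers losses after Post. As ceilings under that allowance:
- Loss implied by the sample size: 154 - 2 x 64 = 26, and 26/154 = 16.9%. Applied to all 308: 52.
- Allowance read as 20% of those recruited: 0.20 x 154 = 30.8, about 31. Applied to all 308: 61.6, about 62.

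If, as an assumption, 10% were lost before Post, the figures would be about 15 of 154 and 31 of 308.

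**Who is affected**

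Section 5.1 has all participants complete Post, 3-month and 6-month assessments, and treats stopping the class separately from leaving the study. Someone who stops attending is therefore still due three PHQ-9 readings. Only those who withdraw from the study, or are lost before Post and not recovered later, have none.

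**Other routes during the classes**

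Section 5.1 provides for consulting the primary provider if a participant is distressed or worsens, for a study phone line, and for instructors to report endorsed suicidality or homicidality. A subset of Gulf War Veterans who discontinue is interviewed within two weeks. Each depends on disclosure or on someone noticing, or reaches only a subset. None is described as yielding a PHQ-9 score, so none can apply the two-category definition.

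The midpoint in Section 6.0 is a single trial-level review. It is not the class Midpoint assessment and supplies no reading during the classes.

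**The case against.** The best defence is that Section 6.0 promises PHQ-9 tracking without saying when, and that one baseline and three later readings are a form of tracking. On that view a reading during the classes is a design preference, and the plan does not contradict itself. This is fair as to wording. It does not change the fact that the defined event cannot be found during the exposure that Section 5.1 names as a risk.

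Several stronger readings are tempting, and the documents do not support them.

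- *Early drop-outs are never measured.* Section 5.1 keeps people who stop the class on the assessment schedule. They are measured late.
- *Nothing but distress calls protects participants during the classes.* Section 5.1 gives other routes, and Section 6.0 has all other adverse events logged whatever the PHQ-9 shows. Decisions on withdrawal for depression are made case by case and are not tied to the PHQ-9.
- *Missing participants count as event-free, so the comparison is biased towards no difference.* The plan does not say how missing scores are treated. They might equally be left out of the denominator, and with unequal loss between arms the bias could run either way.
- *About 31 of 154, or 62 of 308, go unmeasured.* These are ceilings that include losses after Post.

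It is also true that a Week 4–5 reading cannot detect worsening that starts later in the series, nor reach those who have already withdrawn from the study. The remedy is partial. It still gives one reading during exposure where there is now none.

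**Conclusion.** The point holds in a limited form. Section 5.5 and the Abstract agree that no PHQ-9 is scheduled between baseline and Post, so a table-reading error is unlikely. The adverse event defined in Section 6.0 cannot be detected until 8 to about 12 weeks after the first class. Worsening that resolves before Post escapes the definition, and those who leave the study before Post cannot be assessed against it.

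The timing rests only on the plan's own windows. The number without a post-baseline score is unknown. The ceiling of about 26 to 31 of 154 Gulf War Veterans assumes that actual attrition does not exceed the plan and that all of it occurs before Post. No direction of bias in the between-arm comparison can be claimed. The change is worth making because the comparison may bear on stopping and the correction is cheap.

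**What to change.** 1. In Section 5.5, change the PHQ-9 row to B, M, P, 3, 6, and amend the Abstract's account of the Midpoint to match.
2. In Section 6.0, state that the Midpoint PHQ-9 is scored promptly on completion or receipt, that it counts towards the adverse-event definition and the mid-study comparison, and that it is requested from participants who have stopped the class but not withdrawn from the study.
3. In the mid-study comparison, report by arm how many participants have no post-baseline PHQ-9.

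The clinical response to a raised score is for the investigator and is not part of this proposal.

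Cost: an amendment, nine more items on a Midpoint set that already carries nine instruments and is paid, and prompt review by existing staff, including of forms completed away from them. The protocol is at Version 10, dated July 2021, so earlier and later cohorts would be ascertained differently. Each cohort is randomised to both arms, so the difference stays balanced between arms provided the change starts for both arms of a cohort together.
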